11.2.4 PK/QTC

Time-matched ECG measurements and PK samples will be collected after a single dose of SRA737 on Day -7 to Day -4 and during Cycle 1 (See Section 7.7 for the Schedule of Secondary and Exploratory Assessments).

A concentration-effect model will evaluate the relationship between plasma concentrations and the mean change from Baseline in QTcF for all subjects in the PK/QTC study.

Plasma concentrations of SRA737 will be determined using a validated bioanalytical method and summarized using descriptive statistics. Pharmacokinetic parameters, including but not limited to C_{min} , C_{max} , T_{max} , AUC, $t_{1/2}$, total body clearance, and apparent volume of distribution, will be determined using non-compartmental method(s). PK data generated from this study

may be used in conjunction with PK data from other clinical studies in future meta-analyses for population PK assessment. These data will be reported separately.

11.2.5 PHARMACODYNAMICS

11.2.5.1 Tumor Profiling

Archival and/or fresh tumor biopsy samples and blood samples for ctDNA tumor profiling will be obtained at Screening and analyzed using NGS to characterize the mutational status of a pre-specified panel of genes. The proportion of subjects with evaluable tissue and blood based assays will be described. The frequency of each genetic alteration will be characterized. The proportion of subjects with mutations within each of the categories of genetic alterations 1) activating mutations or amplification of growth promoting oncogenes; 2) loss-of-function mutations or deletions in tumor suppressor pathways controlling the G1/S checkpoint; 3) defects in DDR signaling and DNA repair genes; 4) gain of function mutations of replication stress genes will be characterized. The relationship between the presence and type of genetic alteration and clinical outcome (response) will be explored.

11.2.5.2 Exploratory Analyses of ctDNA

Blood will be collected from a subset of approximately 33 subjects for exploratory analyses of ctDNA for mutations relating to resistance to Chk1 inhibitor therapy. Based on the timing and availability of the ctDNA results, a separate statistical analysis plan may be prepared for the analysis of resistance to Chk1 inhibitor therapy.

11.2.5.3 Additional Exploratory Analyses

Blood obtained serially for the purposes of additional exploratory analyses may be analyzed for but not limited to the following: immune profiling, markers of genetic instability including microsatellite instability, neoantigens, and mutational burden.

11.2.5.4 Additional Pharmacodynamic Assays

For subjects who had optional tumor biopsies for additional pharmacodynamic analysis taken at baseline and 2 to 8 hours after dosing at one timepoint from Cycle 1 Day 15 through Cycle 1 Day 22 (inclusive). Inhibition of Chk1 and other PD markers in tumor samples will be measured. Markers to be evaluated include but are not limited to: total Chk1, evidence of DNA damage (pSer296Chk1, pSer317Chk1, and Gamma-H2AX).

Based on the timing and availability of the PDn assay analyses, a separate statistical analysis plan may be prepared for these analyses.

11.3 SAMPLE SIZE

The study will enroll up to 170 subjects in total including an estimated 30–50 subjects during dose escalation and 6 indication-specific expansion cohorts each consisting of approximately 20 prospectively-selected genetically-defined subjects. The sample size for dose escalation is based on assumptions of the likely MTD based on allometric scaling and will depend on the number of dose levels required to establish the MTD and RP2D. The final number of subjects enrolled into the trial will depend on the number of dose levels, the number of subjects who participate in both the Dose Escalation and Cohort Expansion phases, and potentially alternative dose schedules explored.

A sample size of 20 subjects enrolled in each indication-specific expansion cohort will permit confirmation that the 95% confidence intervals around an observed ORR in each cohort is $\pm 16\%$.

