Number of investigational sites:	This is a multicenter study.

Planned number of subjects:	It is estimated that up to 50 subjects will be enrolled into the Dose Escalation Phase of the study. Six cohorts of approximately 20 subjects each (i.e. a total of approximately 120 subjects) will be enrolled into the Cohort Expansion Phase; the final number of subjects enrolled into the trial will depend on the number of dose levels, the number of subjects who participate in both the Dose Escalation and Cohort Expansion phases, and potentially alternative dose schedules explored.
Sample size justification:	The sample size for dose escalation is based on assumptions from allometric scaling and the number of dose levels required to establish the MTD. Six indication-specific expansion cohorts of approximately 20 prospectively-selected genetically-defined subjects each will permit confirmation that the 95% confidence intervals around an observed objective response rate (ORR) in each cohort is $\pm 16\%$.
Study population:	Dose Escalation Phase: Subjects with solid tumors or NHL. Cohort Expansion Phase: Prospectively-selected genetically-defined subjects with metastatic CRC, HGSOC without CCNE1 gene amplification, HGSOC with CCNE1 gene amplification, mCRPC, advanced NSCLC, or HNSCC/SCCA.
Test product, dose, and mode of administration:	SRA737 is a highly potent and selective orally administered checkpoint kinase 1 (Chk1) inhibitor. In this first-in-human trial, the starting dose is 20 mg daily.
Treatment regimen(s):	SRA737 will be administered orally, daily of each 28-day cycle for subjects receiving the continuous dosing schedule. Alternate dosing schedules may also be explored. Subjects may continue to receive treatment as long as none of the treatment discontinuation criteria are met (Section 5.6). Intra-subject dose escalation(s) will be permitted.

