3.8 SUBJECT EVALUABILITY

3.8.1 *DLT EVALUABLE*

All subjects receiving at least 75% of planned doses of SRA737 within Cycle 1 and those subjects receiving less than these planned doses of SRA737 due to DLT will be considered evaluable for dose review decisions.

3.8.2 *REPLACEMENT OF SUBJECTS*

In the Dose Escalation Phase, if agreed by the sponsor, subjects will be replaced if they receive less than 75% of planned doses of SRA737 during the DLT period for reasons other than drug-related toxicity.

In the Cohort Expansion Phase, subjects who are not response-evaluable may be replaced in order to achieve 20 response-evaluable prospectively-selected genetically-defined subjects per indication- specific expansion cohort.

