11.2.3 EFFICACY ANALYSES

The analysis of all efficacy endpoints will be based on the Response Evaluable Population.

Efficacy endpoints will be evaluated using RECIST v1.1 criteria, or for subjects with NHL, the revised IWG criteria ([Cheson 2007](#)), or for subjects with mCRPC, a composite response rate defined as any one of the following ([Scher 2016](#)):

- Best response based on RECIST v1.1
- PSA decrease of $\geq 50\%$

- CTC count conversion

Absolute values for PSA and CTCs will be recorded at baseline and response will be analyzed based on percentage of change.

Descriptive analyses of the distribution of ORR, DCR, DOR, TTR, TTP, PFS per RECIST v1.1, the revised IWG criteria, or a composite of any one of the following:

A) Response based on RECIST v1.1; B) PSA decrease of $\geq 50\%$; or C) CTC count conversion, as applicable, and OS will be prepared.

The ORR will be summarized using binomial proportions and confidence intervals computed by the method of Wilson. The examples below display the CI estimates for response within each indication-specific group of approximately 20 enrolled to an expansion cohort. i.e. at the 95% CI, 0 of 20 responses observed excludes an ORR of 16%.

Numerator	Denominator	Proportion	Lower	Upper
0	20	0	0	0.161
1	20	0.05	0.009	0.236
2	20	0.10	0.028	0.301
3	20	0.15	0.052	0.360
4	20	0.20	0.081	0.416
5	20	0.25	0.112	0.469
6	20	0.30	0.145	0.519
7	20	0.35	0.181	0.567
8	20	0.40	0.219	0.613
9	20	0.45	0.258	0.658
10	20	0.50	0.299	0.701
11	20	0.55	0.342	0.742
12	20	0.60	0.387	0.781
13	20	0.65	0.433	0.819
14	20	0.70	0.481	0.855
15	20	0.75	0.531	0.888
16	20	0.80	0.584	0.919
17	20	0.85	0.640	0.948
18	20	0.90	0.699	0.972
19	20	0.95	0.764	0.991
20	20	1	0.839	1

The distribution of DOR, in the subset of subjects responding will be summarized using Tukey's five number summary, including the minimum, mean, median, maximum and

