## 7. SAMPLE SIZE DETERMINATION

The study will enroll up to 170 subjects in total including an estimated 30–50 subjects during dose escalation and 6 indication-specific expansion cohorts each consisting of approximately 20 prospectively-selected genetically-defined subjects. The sample size for dose escalation is based on assumptions of the likely MTD based on allometric scaling and will depend on the number of dose levels required to establish the MTD and RP2D. The final number of subjects enrolled into the trial will depend on the number of dose levels, the number of subjects who participate in both the Dose Escalation and Cohort Expansion phases, and potentially alternative dose schedules explored. A planned sample size of 20 subjects enrolled in each indication-specific expansion cohort will permit confirmation that the 95% confidence intervals around an observed ORR in each cohort is  $\pm 16\%$ .

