## 9.2. General Data Handling Conventions

#### 9.2.1. Data Displays for Reporting

For tables and figures the data will be displayed as shown in the following tables. Any abbreviation used in the column text will be displayed in full description text in the footnote of the output.

Unless specified otherwise all tables will have corresponding listings supporting the table summaries. The default ordering of the listings is by disease categories, site ID, subject ID, test or parameter name (if applicable), sequence number (AE, medical history, or medication), date of event or date of collection (if applicable).

For study population and efficacy, the columns will be grouped by the primary tumor type regardless if a subject was enrolled under escalation or expansion stage.

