## 11. EFFICACY ANALYSIS

Unless specified otherwise all efficacy analyses will be based on the response evaluable population. An alternative definition of response evaluable population is defined in [Section 8.2](#) and additional efficacy summaries may be repeated using the alternative definition if the differences are deemed clinically meaningful.

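### The ±16% precision claimed for an observed ORR with 20 subjects per expansion cohort is contradicted by the protocol's own Wilson table, where the half-width exceeds 16 points from 4/20 to 16/20

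*Protocol*

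**What the plan says.** The precision statement appears three times:

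- Protocol synopsis, sample size justification: cohorts of approximately 20 "will permit confirmation that the 95% confidence intervals around an observed objective response rate (ORR) in each cohort is" ±16%.
- Protocol Section 11.3: with 20 subjects enrolled per cohort, the "95% confidence intervals around an observed ORR in each cohort is $\pm 16" percent.
- SAP Section 7: a planned 20 enrolled subjects per cohort "will permit confirmation that the 95% confidence intervals around an observed ORR in each cohort is" ±16%.

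None of them gives an assumed ORR, a power, an error rate or any other precision figure.

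The interval method is set in Protocol Section 11.2.3: "The ORR will be summarized using binomial proportions and confidence intervals computed by the method of Wilson". SAP Section 11.1.1 also names Wilson. Section 11.2.3 then prints the 95% limits for every count from 0/20 to 20/20.

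On the denominator, Protocol Section 11.2.3 says "The analysis of all efficacy endpoints will be based on the Response Evaluable Population", and SAP Section 11 agrees: "Unless specified otherwise all efficacy analyses will be based on the response evaluable population". Protocol Section 3.8.2 provides that non-evaluable expansion subjects "may be replaced in order to achieve 20 response-evaluable prospectively-selected genetically-defined subjects" per cohort.

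**The concern.** With no assumed response rate attached, the sentence reads as a general property of 20 subjects: whatever ORR is seen, the 95% interval reaches 16 points either side. For a binomial proportion the width depends on the observed rate, and n = 20 is too small for ±16 points over most of the range. The table in Section 11.2.3 shows this directly.

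ORR is among the primary efficacy endpoints, and this figure is the only quantitative support for the expansion cohort size. Someone who reads only the synopsis or SAP Section 7 is told the precision is better than it is, and the SAP has no table to correct the impression. The sentence in Protocol 11.3 and SAP 7 also counts enrolled subjects, although ORR is analysed in response-evaluable subjects.

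**Working it through.** **Inputs.** n = 20 (Protocol 11.3); two-sided 95% Wilson interval (Protocol 11.2.3, SAP 11.1.1), so z = 1.96 and z² = 3.8415; claimed precision ±16 points.

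**Formula.** With p = x/n and d = 1 + z²/n = 1.19207:

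- centre = (p + z²/2n)/d
- half-width = z·√[p(1−p)/n + z²/4n²]/d, where z²/4n² = 0.0024009

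**Reproducing the protocol's table.**

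- 0/20: centre = 0.09604/1.19207 = 0.0806; half-width = 1.96·√0.0024009/1.19207 = 0.0806; limits 0 to 0.161.
- 4/20: centre = (0.2 + 0.09604)/1.19207 = 0.2483; half-width = 1.96·√(0.008 + 0.0024009)/1.19207 = 0.1677; limits 0.081 to 0.416.
- 10/20: half-width = 1.96·√(0.0125 + 0.0024009)/1.19207 = 0.2007; limits 0.299 to 0.701.

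All 21 printed rows reproduce to three decimals, so the table is sound and the discrepancy lies in the ±16% sentence.

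**Comparison with ±16.** Limits are as printed. Half-width and farther limit are in percentage points, from unrounded limits. Results above 10/20 mirror those below.

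| Responses | Printed 95% limits | Half-width | Distance from ORR to farther limit |
|---|---|---|---|
| 0/20 | 0–0.161 | 8.1 | 16.1 |
| 1/20 | 0.009–0.236 | 11.4 | 18.6 |
| 2/20 | 0.028–0.301 | 13.7 | 20.1 |
| 3/20 | 0.052–0.360 | 15.4 | 21.0 |
| 4/20 | 0.081–0.416 | 16.8 | 21.6 |
| 5/20 | 0.112–0.469 | 17.8 | 21.9 |
| 6/20 | 0.145–0.519 | 18.7 | 21.9 |
| 8/20 | 0.219–0.613 | 19.7 | 21.3 |
| 10/20 | 0.299–0.701 | 20.1 | 20.1 |

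- *± read as half the total width:* above 16 for exactly 4/20 to 16/20, which is 13 of 21 outcomes. The excess is 0.8 points at 4/20, 2.7 at 6/20 and at most 4.1 at 10/20. The largest total width is 40.1 points, against the 32 that ±16 implies.
- *± read as distance from the observed ORR:* the farther limit is more than 16 points away at every count. The excess is only 0.1 at 0/20 and 20/20; elsewhere the distance is 18.6 to 21.9 points.

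**Could another method give ±16?** Half-widths in points:

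| Method (95%) | 3/20 | 4/20 | 6/20 | 10/20 |
|---|---|---|---|---|
| Wald | 15.65 | 17.5 | 20.1 | 21.9 |
| Clopper-Pearson | 17.3 | 19.0 | 21.2 | 22.8 |

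Wald exceeds 16 from 4/20 to 16/20, and Clopper-Pearson from 3/20 to 17/20. Lowering the confidence level to 90% still leaves 17.3 (Wilson) and 18.4 (Wald) at 10/20. Solving the Wald formula for exactly 16 points gives p(1−p) = 0.16²·20/3.8415 = 0.1333, so p ≈ 0.158. The figure therefore fits only an observed ORR near 16% (or 84%), which the documents do not assume.

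**What ±16 would require.** At an ORR of 50%, the Wilson half-width is 16.15 points with 33 subjects and 15.93 with 34. Wald needs 3.8415·0.25/0.16² = 37.5, so 38. This gives scale only; it is not a proposal to enlarge the cohorts.

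**The case against.** The strongest case on the other side accepts the arithmetic and argues that it matters little.

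- *Nothing depends on the figure.* The analyses are descriptive, SAP Section 9.1.2 calls confidence intervals supportive, the actual Wilson interval will be reported, and Section 11.2.3 already prints the right limits. This stands and limits the weight of the point. It does not make the stated precision true.
- *The figure is probably a copying slip.* The text above the Wilson table uses 16% for the upper bound after 0/20, and the printed limit is 0.161. That is a plausible origin, though an inference. A one-sided bound for one outcome is still not a ± precision for any observed ORR.
- *At low response rates the claim is met.* For 0 to 3 responses (and 17 to 20) the half-width is within 16 points. This is correct, so the sentence fails as a general statement and not at every outcome. Even there, the upper limit lies 18.6 to 21.0 points above the observed rate at 1/20 to 3/20.
- *Enrolled versus evaluable is already handled by replacement.* Largely so: Section 3.8.2 aims at 20 evaluable subjects. It is a secondary wording point that the same edit can settle.
- *SAP denominators will not be 20 anyway.* SAP Section 9.2.1 says "the columns will be grouped by the primary tumor type regardless if a subject was enrolled under escalation or expansion stage", and its Table 1 puts both HGSOC cohorts in one column. If both were full and evaluable (n = 40), the largest Wilson half-width would be 1.96·√(0.25/40 + 3.8415/6400)/1.09604 = 14.8 points. In SAP Section 7, then, the sentence is a planning statement about the cohort design and does not describe the reported columns. As a planning statement for 20 subjects it is still wrong.

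**Conclusion.** The concern holds. With 20 subjects, the 95% Wilson half-width is at most about 20 points, not 16, and either limit can lie up to about 22 points from the observed ORR. The overstatement is modest: at most 4.1 points on the half-width and up to 5.9 (21.9 − 16) on the longer arm. It affects the sample-size justification only, not error control, the analysis or any decision. The conclusion assumes a full denominator of 20 and the interval method that both documents specify; the Wald and Clopper-Pearson results show that it does not depend on that method. It should be fixed, because it is the only quantitative reason given for the cohort size and it conflicts with a table in the same protocol.

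**What to change.** Keep n = 20. Replace the ±16% sentence in the synopsis, Protocol Section 11.3 and SAP Section 7 with:

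> With 20 response-evaluable subjects in a cohort, the two-sided 95% Wilson CI has a total width of at most about 40 percentage points (half-width about 20), and either limit may lie up to about 22 points from the observed ORR; for example, 4/20 gives 8.1%–41.6% and 6/20 gives 14.5%–51.9% (see the table in Protocol Section 11.2.3).

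If the 0/20 bound was what the sponsor had in mind, it can be added as its own statement: with no responses in 20, the upper 95% limit is 16.1%.

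The cost is wording in three places, with no change to sample size, analysis or timelines. Two of the edits are in the protocol, and Section 12.1 notes that amendments may need ethics and regulatory review, so they can go in with the next amendment. The stated precision becomes less favourable.

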12 STUDY ADMINISTRATION

This trial is conducted under a clinical trial authorization, and approval from the MHRA and the relevant REC(s), Regulatory Authorities, and ECs/IRBs will be obtained before the start of this trial. This trial is sponsored and monitored by Sierra Oncology and its designee. Applicable regulatory requirements are described in this section.

12.1 PROTOCOL DEVIATIONS AND AMENDMENTS

The protocol should be adhered to throughout the conduct of the study, if a situation arises where the conduct of the study may not be in line with the protocol, the site should contact the Sponsor or Sponsor's designee to discuss this.

Amendments to the protocol may only be made with the approval of the Sponsor. A protocol amendment may be subject to review by the assigned REC(s), Regulatory Authorities (eg, MHRA) and ECs/IRBs Committees. Written documentation must be received before the amendment can be implemented and incorporated into the protocol if necessary.

12.2 SERIOUS BREACH OF GOOD CLINICAL PRACTICE (GCP)

A serious breach is a breach which is likely to effect to a significant degree: the safety or physical or mental integrity of the subjects of the trial, or the scientific value of the trial.

In order that the Sponsor can fulfil their obligations in terms of reporting serious breaches of GCP to the MHRA within seven calendar days of identification, site staff must inform the Sponsor of any unplanned deviations to the trial protocol (or GCP principles) as soon as possible after the deviation occurs to allow prompt evaluation by the Sponsor.

12.3 OBTAINING WRITTEN INFORMED CONSENT

Written informed consent must be obtained from the subject before any protocol specific procedures are carried out.

The subject must be given adequate time to think about their commitment to the study. If new safety information becomes available during the study, subjects must be informed of this and re-consented if appropriate.

Only the site staff with delegated responsibility by the PI, and who have signed the Delegation Log, are permitted to obtain informed consent from subjects and sign the consent form. All signatures must be obtained before the occurrence of any medical intervention required by the protocol (ICH GCP 4.8.8). The date of the signatures of both the subject and the individual obtaining informed consent should be the same.

The delegated site staff member must inform the subject about the background to, and present knowledge of the normal management of their disease and SRA737 and must also ensure that the subject is aware of the following points:

- That SRA737 is new and that the exact degree of activity is at present unknown, but that treating him/her will contribute to further knowledge.
- The known toxicity of SRA737 and the possibility of experiencing side-effects.
- The potential dangers of becoming pregnant (or the subject's partner becoming pregnant) and he/she has been given information about appropriate medically approved contraception (refer to Appendix 4).
- That he/she may refuse treatment either before or at any time during the trial and that refusal to participate will involve no penalty or loss of benefits to which they are otherwise entitled.

- Who to contact for answers to pertinent questions about the research and their rights, and also who to contact in the event of a research-related injury.

A signed copy of the informed consent document (ICD) must be given to the subject to keep and the original ICD, must be filed in the ITF (unless otherwise agreed that the original document will be filed in the medical records and a copy kept in the ITF).

12.4 COMPLETION OF THE ELECTRONIC CASE REPORT FORM

Electronic CRFs approved by the Sponsor will be used to collect the data. The investigator is responsible for ensuring the accuracy, completeness, clarity and timeliness of the data reported in the eCRFs.

Only the investigator and those personnel who have signed the Delegation Log provided by the Sponsor or Sponsor's designee and have been authorized by the investigator should enter or change data in the eCRFs. Authorized users will be included on a user list in order to be provided access to the eCRF. All protocol required investigations must be reported in the eCRF. The investigators must retain all original reports, traces and images from these investigations for future reference.

The collection and processing of personal data from the subjects enrolled in this clinical trial will be limited to those data that are necessary to investigate the efficacy, safety, quality and usefulness of the study drug used in this trial. The data must be collected and processed with adequate precautions to ensure subject confidentiality and compliance with applicable data privacy protection according to the applicable regulations. The data collected will comply with applicable regulation and guidelines on the protection of individuals with regard to the processing of personal data.

Data will be entered directly into electronic screens by authorized site personnel. Amendments to eCRF data will be made directly to the system and the system audit trail will retain details of the original value(s), who made the change, a date and time, and a reason for the change.

Once an eCRF form has been entered by the site personnel, the data are cleaned using manual and automated checks. Queries will be issued electronically to the site. Authorized personnel must answer the queries by making relevant amendments to data and/or providing a response. Answered queries will be closed or reissued as appropriate.

Once the subject is 'off study' and the eCRF has been fully completed, the investigator must provide an electronic signature to authorize the complete subject casebook.

At the end of the trial all eCRFs are retained and archived by the Sponsor and a portable document format copy provided to the investigator who is responsible for archiving at site.

